- Once the EEG technologist has finished their typical clinical set-up, live EEG data will start streaming to a non-blinded EEG reader (an epileptologist or a neurologist with special interest in EEG) at a remote location for interpretation.
- Based on the EEG reader's live report(s) to the ICU team, anaesthetic(s) may be changed
 - If the ICU elects to make no anaesthetic changes, then tDCS shall be applied right away
 - If the ICU elects to increase or decrease anaesthetic, then another 10 minutes shall elapse for the anaesthetic change to take effect prior to tDCS application
- During real-time tDCS application, the EEG reader will determine efficacy by assessing whether there has been enough improvement in the frequency and severity of epileptiform activity (primary study outcomes #1 and #2) to warrant discontinuation (or continued discontinuation) of intravenous anaesthetic sedation to the end of the EEG recording (secondary study outcome)
 - Frequency of epileptiform activity (primary outcome #1) is defined as the number of discharges per unit time (e.g. spikes per minute)
 - Severity of epileptiform activity (primary outcome #2) is defined by the morphology of the activity as outlined by the American Clinical Neurophysiology Society Standardized Critical Care EEG Terminology for the interictal-ictal continuum (e.g. spikes or sharp waves are more epileptiform than broad sharp waves or sharply contoured activity)
 - If tDCS unexpectedly worsens epileptiform activity, tDCS will be terminated immediately
- After tDCS application is complete, the RA will remove all tDCS equipment from the patient and the bedside
- The EEG reader will continue live-monitoring the study to ensure that any changes in the frequency and/or severity of epileptiform activity are enduring (i.e. persist through to the end of EEG recording)
- Total EEG recording will be 3 hours as per the usual maximum ICU EEG recording duration protocol

3. Statistical Analysis Plan

- The primary study outcomes of epileptiform activity frequency before, during, and after tDCS will be analyzed on a per-stimulation session basis
- The primary study outcomes of epileptiform activity frequency before, during, and after tDCS will also be analyzed on a per-patient session basis by averaging spike rates for all sessions in that patient
- All data will be assessed for normality using the Shapiro-Wilk test

- Parametric tests will be used for normally distributed data and non-parametric tests will be used for non-normally distributed data in order to test before vs. during tDCS on per-session and per-patient bases; and before vs. after tDCS on per-session and per-patient bases

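### Only an anaesthetic change is given time to act before tDCS, and the analysis ignores other antiseizure drugs, so the effect of an added drug could be counted as a tDCS effect

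*Combined protocol and SAP*

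**What the plan says.** Section 2.iii (Real-Time Anaesthetic Management) names one kind of treatment response to the live EEG: "Based on the EEG reader's live report(s) to the ICU team, anaesthetic(s) may be changed". Two branches follow. In the first, "If the ICU elects to make no anaesthetic changes, then tDCS shall be applied right away". In the second, if anaesthetic is raised or lowered, "another 10 minutes shall elapse for the anaesthetic change to take effect prior to tDCS application".

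The first primary outcome is a rate: "Frequency of epileptiform activity (primary outcome #1) is defined as the number of discharges per unit time (e.g. spikes per minute". Section 3 states: "The primary study outcomes of epileptiform activity frequency before, during, and after tDCS will be analyzed on a per-stimulation session basis". It adds a per-patient version that averages the spike rates over all of a patient's sessions. The tests are chosen by normality, "in order to test before vs. during tDCS on per-session and per-patient bases; and before vs. after tDCS on per-session and per-patient bases".

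Neither the protocol sections nor the analysis plan mentions non-anaesthetic antiseizure drugs. Nothing says that they are held constant, recorded, used to set a session aside, or adjusted for. The start and length of the before window are not defined.

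**The concern.** The 10-minute wait shows that the authors saw the problem in principle: a treatment given in response to the EEG report can itself change the EEG, and should act before stimulation starts. The same reasoning applies to any drug given to suppress epileptiform activity, but the rule is limited to anaesthetic. A session in which another antiseizure drug is added while anaesthetic is left alone meets the condition for immediate stimulation. The drug could then take effect inside the during or after window, while the before window was recorded without it.

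Each session is its own only comparator, so the analysis cannot separate the two effects. An added or increased drug is meant to lower the discharge rate, so the error would tend to favour tDCS. The per-patient averages include every session and carry the error with them. At stake is whether a fall in the primary outcome can be attributed to tDCS.

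**Working it through.** **No figure to reproduce.** The documents give no sample size, SD, effect size, alpha or power.

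**Exposure time, from the documents.** Stimulation lasts 20 minutes (section 2.ii) and the total recording is 3 hours (section 2.iii). That leaves 180 − 20 = 160 minutes for the before and after windows together. The split is not stated. If the after window takes most of that time, a drug has more opportunity to act in the before-after contrast than in the before-during contrast.

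**Size, by assumption.** Let the true tDCS effect be zero. A share f of sessions receives a drug that lowers the rate by a fraction d, and the within-session log rate ratio has SD s in unaffected sessions. Then:

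- Mean log ratio = f × ln(1 − d); apparent fall = 1 − (1 − d)^f.
- With d = 0.5: 1 − 0.5^0.1 = 6.7%; 1 − 0.5^0.2 = 12.9%; 1 − 0.5^0.3 = 18.8%.

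The chance of a significant result (one-sample t-test on the log ratios, two-sided 5%) was simulated with 20,000 replicates per setting, s = 0.6 and n = 40 independent sessions:

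| Share affected | Drug-induced fall 50% | Drug-induced fall 30% |
|---|---|---|
| 10% | about 10% | about 7% |
| 20% | about 25% | about 11% |
| 30% | about 47% | about 19% |

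Hand check of the 20%, 50% cell:

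- Mean = 0.2 × ln 0.5 = −0.139.
- Variance = 0.36 + 0.2 × 0.8 × (ln 0.5)² = 0.36 + 0.077 = 0.437, so SD = 0.661 and SE = 0.661/√40 = 0.105.
- Ratio of mean to SE is about 1.33 in absolute value. Against a critical value of 2.02, the rejection chance is about 24% to 25%, in line with the simulation.

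**Sensitivity to the assumptions.** With 20% affected and a 50% fall, the figure is about 14% at s = 0.9 and about 41% to 42% at s = 0.4. At s = 0.6 and 80 sessions it is about 46%, so more sessions do not remove the bias. A separate simulation with s = 0.5 gave:

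| Share affected | Drug-induced fall | n = 20 | n = 50 |
|---|---|---|---|
| 10% | 50% | 8% | 13% |
| 25% | 25% | 9% | 16% |
| 25% | 50% | 23% | 54% |

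With no affected sessions the rate was about 5% throughout.

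**Limits of the illustration.** Sessions are treated as independent. With up to 10 sessions per patient (section 2.ii), 40 sessions could come from as few as 40/10 = 4 patients. The per-patient analysis was not simulated.

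**The case against.** The strongest reply is that the triggering event is not documented. Section 2.i lists four reasons for the EEG, and all are framed around anaesthetic. Section 2.iii names anaesthetic as the treatment that may change on the live report. The response that the protocol foresees is therefore the one its rule covers, and the number of other drug changes during a recording could be near zero. This stands: frequency and size cannot be taken from the documents.

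Three stronger readings are tempting and are not supported:

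- **That the plan classes these sessions as clean and credits their drug effect to tDCS.** The rule sets when stimulation starts; it does not label sessions for analysis. Section 3 pools all sessions and has no stratum of unchanged anaesthetic. Such a group would exist only if someone later split the analysis by anaesthetic status.
- **That the bias always favours tDCS in both contrasts.** It does so only for an added or increased drug whose effect falls after the before window and inside the window compared. That window is undefined, a late-acting drug could miss the 20 minutes of stimulation, and a reduction could act in the opposite direction.
- **That the simulated rates describe this trial.** Every input is assumed.

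One could also call this merely a case of the general weakness of an uncontrolled before-after design. That is fair, but this part of the weakness can be measured from records and addressed in the analysis.

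**Conclusion.** The concern holds as a conditional one. The pre-stimulation wait is tied to anaesthetic only, other antiseizure drugs are not mentioned, and the contrasts have no control and no adjustment. If a non-anaesthetic antiseizure drug is started, loaded or increased between the before window and the end of recording, its effect could be counted as a tDCS effect.

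The mechanism follows from the design; the size does not. Under the assumptions shown, the distortion runs from slight (10% of sessions affected, 30% drug-induced fall: about 7% false-positive rate against a nominal 5%) to serious (30% affected, 50% fall: about 47%). Because the frequency is unknown, the right response is to record it and to prespecify what the analysis does with it.

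**What to change.** Change the analysis plan only. No change to care, dosing or the timing of stimulation is proposed.

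1. Define the start and end of the before, during and after windows.
2. From the ICU medication record, abstract the time, type and direction of every non-anaesthetic antiseizure drug change, from the start of the EEG (or a short prespecified interval before it) to the end of recording.
3. Keep the all-session analysis. Beside it, prespecify both contrasts, per session and per patient, excluding from each contrast the sessions with a drug change between the start of the before window and the end of the window compared.
4. Report the number of sessions affected in each contrast. State that efficacy will not be claimed from the pooled result alone if the two analyses disagree.
5. Do not cut the after window at a later drug as the main rule. A drug given because activity returns would remove the period of failure, and section 2.iii asks whether changes last until recording stops. Show these sessions separately, or count the added drug as non-persistence in a sensitivity analysis.

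Excluding sessions for a drug given after stimulation starts is also selective, so the restricted analysis should stand beside the full one and not replace it. A long look-back such as 12 hours is better avoided as an exclusion rule: it would discard sessions whose drug effect is already present in the before window.

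The cost is chart abstraction, a few sentences in section 3, and less precision in the restricted analysis; how much less depends on how many sessions are affected.
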